#### 3.5.4 Treatment Failures

Failure to implant the DESyne X2 stent at the intended target site will be recorded as a treatment failure on the case report form. In the event of the inability to treat the lesion with the study stent, the physician may treat the patient according to his/her medical judgment with another approved device. These patients should receive standard antiplatelet therapy.

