### 3.5.7 Other Follow-up Guidelines

There may be situations where an attempt to treat the patient with the DESyne X2 stent is made, but the procedure is stopped prior to the stent being delivered to the target site (i.e., the stent is introduced into the guiding catheter and circulation but patient becomes unstable, power outage, etc.). In these situations, the patient will be deregistered from the study and treated per standard hospital practice.

In the situation where an attempt to treat the patient with the DESyne X2 stent is made but due to a device malfunction or failure to cross the lesion, no DESyne X2 stent is subsequently implanted, the case shall be noted as not meeting the Device Success endpoint. All device failures will be recorded and reported.

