## 4.0 ENDPOINTS

The following endpoints chosen for the post market clinical follow-up evaluation are the recognized professional and industry standards in determining performance of drug eluting stents in interventional cardiology.

- Acute Device Success: attainment of final result with < 50% residual stenosis of the target site, using a DESyne X2 stent and standard pre-dilation catheters and post-dilatation catheters (if applicable)

Physician feedback will be obtained for the following device characteristics:

- Device preparation
- Lesion access and cross
- Stent expansion
- Delivery system removal
- Stent crossability for post-dilatation as required
- Device malfunction assessment

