#### **5.0 EARLY WITHDRAWAL FROM THE STUDY**

Following the introduction into the body of the intended device, all patients are considered enrolled into the study. Patients will be exempt from only if they withdraw their consent or the physician withdraws them from the study.

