#### **6.0 STATISTICAL CONSIDERATIONS**

This Post Marketing Clinical Follow-up (PMCF) study is designed to confirm the performance of the DESyne X2 Novolimus Eluting Coronary Stent System with regards to the residual risks of lesion access and acute device implantation through visually-assessed angiographic endpoints and physician feedback and demonstrate that these characteristics are not different than the DESyne Novolimus Eluting CSS. The overall result of this study will be summarized descriptively, and examined relative to the clinical results observed in the EXCELLA II Randomized Study.

Data for all categorical endpoints will be summarized with patient counts, percentages, and exact 95% Clopper-Pearson confidence intervals.

One study population will be examined during the analyses: the modified intent-to-treat population (MITT), which will consist of all patients treated with at least one DESyne X2 stent.

While this post marketing study is not powered to determine extremely rare events, a sample size of 100 patients is sufficient to detect rare, acute device related performance issues.

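### The only analysis population, read as implanted patients, leaves out of the Device Success rate the no-implant failures that Section 3.5.7 scores against it

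*Combined protocol and SAP*

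**What the plan says.** Enrolment is set in Section 5.0: "Following the introduction into the body of the intended device, all patients are considered enrolled into the study". This point comes before implantation.

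Section 3.5.7 scores the attempts that fail. It begins "In the situation where an attempt to treat the patient with the DESyne X2 stent is made but due to a device malfunction" (failure to cross is the other cause named) and concludes that if "no DESyne X2 stent is subsequently implanted, the case shall be noted as not meeting the Device Success endpoint". The same section has all device failures recorded and reported, but gives no denominator for that report. Section 3.5.4 adds: "Failure to implant the DESyne X2 stent at the intended target site will be recorded as a treatment failure on the case report form".

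Section 6.0 names a single population for the analyses: "the modified intent-to-treat population (MITT), which will consist of all patients treated with at least one DESyne X2 stent". Every categorical endpoint is to be given as counts, percentages and exact 95% Clopper-Pearson intervals. No second population appears anywhere.

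Section 4.0 lists Acute Device Success and then says: "Physician feedback will be obtained for the following device characteristics". The list that follows includes lesion access and crossing, and device malfunction.

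**The concern.** A patient in whom the X2 could not cross, or malfunctioned, and who ends with no X2 stent is enrolled under Section 5.0 and is a Device Success failure under Section 3.5.7. If the MITT means implanted patients, that patient is not in the only population analysed, so the scoring rule in Section 3.5.7 has no effect on the reported rate.

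The stent, drug and polymer are the same as on the earlier DESyne. What is new is the delivery system, and the stated purpose concerns lesion access and acute implantation. A no-implant failure is the most direct bad outcome on that question. The rate would be conditioned on the device having been delivered and would then be set beside EXCELLA II results as evidence about delivery. If the feedback items are also reported as percentages, the same rule would remove these patients from the figures for lesion access and malfunction.

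**Working it through.** **Does the MITT mean implanted patients?** Section 6.0 does not define the term. Two other places bear on it. Section 3.5.7 describes cases with no implant as an attempt to treat. Section 3.5.4, dealing with failed implantation, says: "In the event of the inability to treat the lesion with the study stent". A patient whose lesion could not be treated with the study stent is not naturally one treated with at least one such stent. Implanted is the natural reading, and nothing in Section 6.0 extends the population to attempts.

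**Direction of the effect.** Let N be the patients with the device introduced, f those with no X2 implanted because of malfunction or failure to cross, and s the implanted successes. The MITT rate is s/(N − f). The rate that follows Section 3.5.7 is s/N. For any f > 0 and s > 0 the first is larger, so the effect has one sign.

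**Inputs.** N = 100 is the planned maximum (Section 6.0). The interval method is Clopper-Pearson (Section 6.0). The documents give no value for f, so f = 1 to 5 is assumed. Also assumed: nobody is deregistered, and every implanted case has less than 50% residual stenosis, so s = 100 − f.

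**Formula.** For x successes in n, the lower limit is the 2.5% quantile of Beta(x, n − x + 1) and the upper limit is the 97.5% quantile of Beta(x + 1, n − x). When x = n, the lower limit reduces to 0.025^(1/n) and the upper limit is 100%.

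| f (assumed) | MITT rate (95% CI) | All introduced (95% CI) |
|---|---|---|
| 1 | 99/99 = 100% (96.34 to 100) | 99/100 = 99% (94.55 to 99.97) |
| 2 | 98/98 = 100% (96.31 to 100) | 98/100 = 98% (92.96 to 99.76) |
| 3 | 97/97 = 100% (96.27 to 100) | 97/100 = 97% (91.48 to 99.38) |
| 4 | 96/96 = 100% (96.23 to 100) | 96/100 = 96% (90.07 to 98.90) |
| 5 | 95/95 = 100% (96.19 to 100) | 95/100 = 95% (88.72 to 98.36) |

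The MITT column hardly moves as failures accumulate. From f = 4 the all-introduced rate is below the MITT lower limit (96.00 < 96.23). At f = 3 it is still inside (97.00 > 96.27).

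The pattern does not need perfect implanted results. With f = 3 and one failure among the implanted, the MITT gives 96/97 = 98.97% (94.39 to 99.97) and all introduced gives 96/100 = 96% (90.07 to 98.90).

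**The plan's own figure.** Section 6.0 calls 100 patients sufficient to detect rare acute device problems. It states no rate, power or margin, so the figure cannot be reproduced. The chance of at least one event in 100 is 1 − (1 − p)^100: 63.4% for p = 1%, 86.7% for 2%, 95.2% for 3% and 99.4% for 5% (p assumed). Such events are therefore likely to occur at these rates. On the implanted reading, none of the no-implant kind would count in the Device Success rate.

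**The case against.** The strongest reply is that the conflict depends on an undefined phrase. Section 3.5.7 gives a specific rule for these cases, and that rule has most purpose if they count in the rate, so the two sections could be read together as including attempts. Also, Section 3.5.4 speaks of treating a lesion, while Section 6.0 speaks of patients. This reading is possible, but Section 6.0 does not state it and the protocol's usage leans the other way. If it was intended, the text still has to say so.

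Several narrower points stand:

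- The failures are recorded and reported, so they would be detected in the ordinary sense. The sample-size statement is not refuted. But a listing does not correct a percentage or its interval.
- Only patients who end with no X2 stent at all are affected. Someone rescued with a second X2, or with another lesion successfully stented, stays in the MITT.
- The number of failures is assumed throughout. The crossing at four compares a point estimate with an interval from largely the same patients, and is not a decision rule.
- The protocol gives no scale for the feedback items and does not say outright that they will be reported as percentages. The extension to them is an inference from Section 6.0 having one population and from the protocol summary listing them as key endpoints.
- A failure during preparation, before introduction into the body, falls outside an all-introduced set as well.

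**Conclusion.** The concern holds. On the natural reading of Section 6.0, the headline rate and its interval omit enrolled patients whom Section 3.5.7 declares to be failures, and the omission can only favour the device. With every implanted case a success, the overstatement equals the proportion of no-implant failures: 1 to 5 percentage points for an assumed 1 to 5 failures in 100. The lower limit is then 96.2 to 96.3% where it should be 94.6% down to 88.7%. If there are no such failures, the two analyses coincide.

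The conclusion rests on reading the MITT as implanted patients, and its size on assumed counts. There is no hypothesis test or threshold, so no formal decision changes. It should be fixed because the rate and its interval are the study's main quantitative result on the question it asks.

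**What to change.** In Section 6.0:

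1. Make the main Device Success population all enrolled patients in whom an X2 system was introduced (the Section 5.0 enrolment point). Count a malfunction or failure to cross with no X2 implanted as a failure, as Section 3.5.7 already directs.
2. Leave out only patients deregistered under Section 3.5.7 for reasons unrelated to the device, and list each with the reason. Section 5.0 also allows a patient to leave if "the physician withdraws them from the study", so state how a patient withdrawn after a failed attempt is counted.
3. Use the same set for the delivery characteristics that can be rated without an implant, such as lesion access and crossing and device malfunction. Report preparation failures that occur before introduction separately.
4. Define the MITT explicitly as implanted patients and keep it as a supportive analysis.
5. State which denominator the EXCELLA II figure uses. Section 2.1 reports one Phase 2 result on an MITT basis, but that is a 60-month composite for DESyne BD with the term undefined, so it does not settle the denominator for acute success. If the historical rate does use implanted patients, compare it with the supportive MITT rate.

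The cost is wording in Section 6.0, consistent with Sections 3.5.7 and 5.0, and a check of the historical denominator. Sections 3.5.4 and 3.5.7 already require these failures to be recorded, so no new data are needed. The reported rate may be slightly less favourable.

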## 1.0 DESyne X2 PMCF PROTOCOL SUMMARY

Design:	Prospective, non-randomized, multicenter, international Post Marketing Clinical Follow-up (PMCF) study				
Enrollment:	Enrollment of up to 100 patients with up to three de novo native coronary artery lesions measuring between 2.25 and 4.0 mm in diameter and $\leq 34$ mm in length receiving the DESyne X2 Novolimus Eluting Coronary Stent System (CSS).				
Clinical Site Locations:	Drawn from up to 10 International Sites				
Objective and Rationale:	
To confirm the performance of the DESyne X2 Novolimus Eluting Coronary Stent System with regards to the residual risks of lesion access and acute device implantation through visually-assessed angiographic endpoints and physician feedback and demonstrate that these characteristics are not different than the DESyne Novolimus Eluting CSS.
 
A single-arm study comparing the DESyne X2 PMCF data to the historic DESyne acute performance data will confirm that the DESyne X2 delivery system performs similarly to the DESyne delivery system.
				
Key Endpoints:	
Acute Device Success: attainment of final result with <math>< 50\%</math> residual stenosis of the target site, using a DESyne X2 stent and standard predilatation catheters and post-dilatation catheters (if applicable)
 
Device preparation
 
Lesion access and cross
 
Stent expansion
 
Delivery system removal
 
Stent crossability for post-dilatation as required
 
Device malfunction assessment
				
Time Course:	
 
 Initial Enrollment	Q3 2020	
 
 Enrollment Complete	Q2 2021	
 
	Initial Enrollment	Q3 2020	Enrollment Complete	Q2 2021
Initial Enrollment	Q3 2020				
Enrollment Complete	Q2 2021				
Inclusion Criteria:	
Candidates for this study must meet all of the following criteria:
 
 
1) The patient must be <math>\geq 18</math> years of age.
 
2) The patient must have stable angina pectoris as defined by the Canadian Cardiovascular Society Classification, documented silent ischemia, acute coronary syndrome, or a positive functional study requiring treatment
 
3) The patient is considered a candidate for coronary stent implantation and has a planned intervention of up to
 
				

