### 2.5 Summary of Study Design

This PMCF study will enroll up to 100 male and female patients with up to two *de novo* native coronary artery lesions who satisfy all entry criteria. Study endpoints will be summarized.

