### 3.0 MATERIALS AND METHODS

#### 3.1 Selection of Subjects

The study will include up to 100 male and female patients all with *de novo* native coronary artery lesions who meet eligibility criteria and agree to participate in the trial. Sites may enroll up to a maximum of 40 patients per site, or 40% of the total number of enrolled patients.

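### Section 6.0 calls 100 patients enough to detect rare acute device issues without giving a rate or calculation; per patient, a 95% chance of seeing one event needs a true rate of about 3%

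*Combined protocol and SAP*

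**What the plan says.** Section 6.0 justifies the sample size in one two-part sentence. The first part concedes that "this post marketing study is not powered to determine extremely rare events". The second asserts that "a sample size of 100 patients is sufficient to detect rare, acute device related performance issues". No event rate is attached to either class of event, and there is no detection probability, precision target or calculation.

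The section plans a descriptive summary, examined against the EXCELLA II results, and specifies "exact 95% Clopper-Pearson confidence intervals" for categorical endpoints. The single analysis population (MITT) consists of patients who received one or more study stents.

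Elsewhere, 100 appears as an upper bound. The Protocol Summary has "Enrollment of up to 100 patients", Section 2.5 has "This PMCF study will enroll up to 100 male and female patients" and Section 3.1 has "The study will include up to 100 male and female patients". No minimum is stated.

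**The concern.** The study's stated purpose is to confirm performance with regard to the residual risks of lesion access and acute implantation. How small a problem the study could reveal is therefore a central property of the design, and the Section 6.0 sentence is the only place where the plan describes it.

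A reader cannot tell from that sentence where *extremely rare* ends and *rare* begins, or how likely a *rare* problem is to show up. If *rare* has an everyday meaning of 1% or less, 100 patients have a substantial chance of showing no event at all. The risk is that a clean result is read beside an assurance of sufficiency that the plan has not supported.

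**Working it through.** **Inputs**

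- n = 100 patients (Section 6.0), stated as a maximum in the Protocol Summary and Sections 2.5 and 3.1.
- Interval method: exact 95% Clopper-Pearson (Section 6.0), taken as two-sided, its usual meaning.
- Rate meant by *rare*: not stated. Assumed range: 0.1% to 5% per patient.
- Detection probability: not stated. Assumed values: 80%, 90% and 95%, with detection taken as seeing at least one event.

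**Can the plan's figure be reproduced?** No. There is no rate or probability from which to derive 100. A 95% chance of one event at a true rate of 3% needs ln(0.05)/ln(0.97), rounded up to 99. That is close to 100, but the plan states neither 3% nor 95%, so this is not a reproduction.

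**Step 1. Chance of at least one event in 100 patients:** 1 − (1 − p)^100

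| True rate p | Chance of ≥1 event |
|---|---|
| 0.1% | 9.5% |
| 0.5% | 39.4% |
| 1% | 63.4% |
| 2% | 86.7% |
| 3% | 95.2% |
| 5% | 99.4% |

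At 1%, for example, 1 − 0.99^100 = 0.634. One event is a lenient standard: the chance of two or more events is 26.4% at 1% and 80.5% at 3%.

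**Step 2. Lowest rate detected with probability g:** p = 1 − (1 − g)^(1/100)

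- g = 95%: 1 − 0.05^(1/100) = 2.95%
- g = 90%: 1 − 0.10^(1/100) = 2.28%
- g = 80%: 1 − 0.20^(1/100) = 1.60%

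**Step 3. Upper limit if no event is seen:** 1 − 0.025^(1/100) = 3.62%. This exceeds the 2.95% in Step 2 because a two-sided 95% interval places 2.5%, not 5%, in the upper tail.

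**Step 4. Patients needed for a 95% chance of one event:** ln(0.05)/ln(1 − p), rounded up, gives 149 at 2%, 299 at 1% and 598 at 0.5%. These show the scale of the gap and are not a proposal to enlarge the study.

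**Step 5. Dependence on n.** The same formulas apply to whatever number is analysed. For illustration only, with 90 patients the 95% threshold is 1 − 0.05^(1/90) = 3.27% and the zero-event limit is 1 − 0.025^(1/90) = 4.02%.

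**Step 6. Which patients count.** Under Section 3.5.7, a device malfunction or failure to cross with no study stent implanted is noted as not meeting Device Success. Under Section 6.0, a patient with no study stent is outside the MITT population. The figures above hold for such failures only if those patients are included in the count.

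**The case against.** The strongest reply is that the sentence is qualified and its key word is undefined. The plan disclaims extremely rare events. If *rare* was meant as roughly 3%, 100 patients give a 95.2% chance of seeing one event and the sentence is true. This stands to the extent that a reader might infer an arithmetic error, and the documents do not show one: they contain no calculation that could be wrong. It does not rescue the assurance, because with neither term quantified nobody can tell what was disclaimed and what was claimed.

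A reader might also infer that the sponsor will treat a run without failures as excluding rare problems. The plan does not say so. It speaks of detecting, not excluding, and the planned exact intervals would show the 3.6% limit beside a 0/100 result. The gap lies in the stated design capability, not in the planned reporting. No test, margin or decision rule depends on the sentence.

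Per-patient counting is not the only possibility. Patients may have up to three lesions (Protocol Summary, Sections 3.2 and 3.5.2; Section 2.5 says two), and a delivery problem can occur at each device use. If uses were independent, the 95% threshold would be 1 − 0.05^(1/150) = 2.0% at 150 uses and 1 − 0.05^(1/300) = 1.0% at 300. But the plan gives no expected lesion count, independence within a patient is not established, and Section 6.0 argues from patients.

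Finally, 100 is probably the intended size. Section 6.0 names it as the sample size, and the two site limits in Section 3.1 (40 patients, or 40% of the total) coincide at exactly 100. A reader might infer from the *up to* wording that a much smaller study or an early closure is foreseen. The documents provide for neither. What remains is that the claim depends on a number the enrolment statements give only as a maximum.

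**Conclusion.** The claim of sufficiency is unsupported and undefined, and it fails for true per-patient rates clearly below 3%. At 1% there is a 37% chance of seeing nothing (100 − 63.4 = 36.6); at 0.5% it is 61% (100 − 39.4 = 60.6).

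This rests on four assumptions: counting per patient, taking one event as detection, reaching the full 100, and including attempted cases that end without an implant. Reading reliable detection as 90% or 80% lowers the threshold to 2.3% or 1.6%, which is still above 1%.

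This is a should-fix point. It concerns what the plan says the study can show. It does not invalidate the descriptive analysis or show that the study is too small for its descriptive purpose.

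**What to change.** In Section 6.0, replace the sentence with wording such as:

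> With 100 patients the study has a 95% chance of observing at least one event of a type with a true per-patient rate of about 3% or higher (80% at 1.6%, 63% at 1%). If none is observed, the exact two-sided 95% upper limit is 3.6%, and rarer issues cannot be excluded. These figures apply to all patients in whom the device was attempted, including device failures with no implant.

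Also:

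- name 100 as the planned number in the Protocol Summary and Sections 2.5 and 3.1;
- restate the figures in the report for the number actually analysed;
- count failures without an implant in the analysis, since the MITT definition alone would leave them out and the replacement sentence would then overstate detection.

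The cost is editing, with no extra patients or procedures. The stated capability becomes less favourable than the present wording suggests.

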## **7.0 DATA MONITORING AND QUALITY CONTROL**

### **7.1 Required Data**

All required data for this trial will be collected using Case Report Forms (CRF). Only authorized personnel will be permitted to enter data on the CRFs. The computerized handling of the data by the sponsor and/or designee after receipt of the CRFs may generate additional requests to which the investigator is obliged to respond by confirming or modifying the data questioned.

### **7.2 Training**

The training of appropriate clinical site personnel will be the responsibility of the study sponsor, Elixir Medical, or their appointed designee.

### **7.3 Logs and Case Report Forms**

An authorized signature log, screening log, protocol deviation log, and issues log will be maintained by the investigative site and be available for review by the sponsor when requested. All appropriate CRFs should be completed as soon as possible after enrollment or follow-up contact with the patient. Submission of the CRFs will be coordinated between the investigative site and the data management group. This includes coordination of data discrepancy forms.

